## **12 SPECIAL REQUIREMENTS AND PROCEDURES**

This protocol was designed and will be conducted, recorded, and reported in compliance with the principles of Good Clinical Practice (GCP). These requirements are stated in “Guidance for Good Clinical Practice,” International Conference on Harmonization (ICH) of Technical Requirements for Registration of Pharmaceuticals for Human Use and national regulations.

### **12.1 INSTITUTIONAL AND ETHICAL REVIEW**

This protocol and patient informed consent form must be reviewed and approved by an IRB or IEC complying with the national regulations and the guidelines of the ICH before enrollment of patients. A copy of the letter or certificate of approval from the IRB or IEC and the approved consent form must be received by Genzyme prior to initiation of the study.

### **12.2 CHANGES TO THE CONDUCT OF THE STUDY OR PROTOCOL**

No change in the study procedures, except to eliminate an immediate hazard, shall be effected without the mutual agreement of the Investigator and Genzyme. All changes must be documented by signed protocol amendments. If changes to the design of the study are made, the amendment must be submitted to and approved by the IRB, IEC, or any other appropriate regulatory authority, signed by the Investigator, and returned to Genzyme.

### **12.3 INVESTIGATOR'S RESPONSIBILITIES**

#### **12.3.1 Patient Informed Consent**

Before a patient's participation in the clinical trial, study informed consent forms for mother and parents/legal guardian, where required by law separate genetic informed consent forms for mother and parents/legal guardian will be signed and personally dated by the patient or by the patient's legally acceptable representative, and by the person who conducted the informed consent discussion. A copy of each signed and dated written informed consent form will be provided to the patient.

The informed consent form and where required by law the separate genetic informed consent form used by the investigator for obtaining the patient's informed consent must be reviewed and approved by the sponsor before submission to the appropriate ethics committee (IRB/IEC) for approval/favorable opinion. Upon approval by the IRB or IEC, the Investigator must furnish the Sponsor with: (1) a photocopy of the approved informed consent and (2) a copy of the letter stating formal approval has been granted by the institution, prior to initiation of the study.

Signed, written informed consent from the infant's parent(s) or legal guardian(s) is required prior to enrollment in the study. It is the responsibility of the Investigator to obtain such consent.

### **12.3.2 Case Report Forms**

CRFs will be filled out legibly and completely (black ballpoint pen). Refer to Section 10.1 for further guidance on completion of CRFs.

The original CRFs will be provided to Genzyme. A copy of the CRFs will be maintained in the Investigator's file. Designated site personnel must complete CRFs in a timely manner.

Illegible or incomplete entries will be returned and queried to the Investigator for clarification.

Patient records in connection with the study, including patient charts, laboratory data, etc. will be made available to Genzyme for review.

### **12.3.3 Record Retention**

The investigator must maintain confidentiality of all study documentation and take measures to prevent accidental or premature destruction of these documents.

The investigator should retain the study documents at least 15 years after the completion or discontinuation of the clinical trial.

However, applicable regulatory requirements will be taken into account in the event that a longer period is required.

The investigator must notify the sponsor before destroying any study essential documents following the clinical trial completion or discontinuation.

If the investigator's personal situation is such that archiving can no longer be ensured by him/her, the investigator shall inform the sponsor and the relevant records shall be transferred to a mutually agreed upon designee.

### **12.3.4 Monitoring**

A representative of Genzyme will visit the Investigator periodically for the purpose of monitoring the progress of this study in accordance with national regulations and ICH-GCP guidelines. It is the responsibility of the Investigator to be present or available for consultation during such scheduled monitoring visits. During these routine visits, all data pertaining to a patient's participation in this clinical investigation must be made available to the monitor.

Genzyme personnel or their designee may perform an audit at any time during or after completion of the clinical study. All study-related documentation must be made available to the designated auditor.

In addition, a representative of a regulatory agency may choose to inspect a study center at any time prior to, during, or after completion of the clinical study. A Genzyme representative will be available to assist in the preparation for such an inspection. All pertinent study data should be made available to the regulatory authority for verification, audit, or inspection purposes.

### **12.3.5 Materials Control**

There will be no clinical trial supplies provided for this study.

For specific information concerning warnings, precautions, and contraindications, the Investigator is asked to refer to the appropriate section of the Investigator Brochure and/or product labeling. Because of the possibility of AEs, a fully equipped emergency cart, or equivalent supplies and equipment, and personnel competent in recognizing and treating adverse reactions of all types should be immediately available.

### **12.3.6 Disclosure of Data**

All information obtained during the conduct of this study will be regarded as confidential and written permission from Genzyme is required prior to disclosing any information relative to this study. Manuscripts prepared for publication will be in accordance with the policy previously presented by Genzyme to the Investigator. Submission to the Sponsor for review and comment prior to submission to the publisher will be required. This requirement should not be construed as a means of restricting publication, but is intended solely to assure concurrence regarding data, evaluations, and conclusions and to provide an opportunity to share with the Investigator any new and/or unpublished information of which he/she may be unaware.

### **12.3.7 Clinical Study Report**

If deemed appropriate by the Sponsor, an Investigator may be designated to sign the completed clinical study report at the end of this study.

1 OVERVIEW AND INVESTIGATIONAL PLAN

1.1 STUDY DESIGN AND RANDOMIZATION

This is a phase 4, multicenter, multinational study of the potential effects of Fabrazyme on lactation and on the growth, development, and immunologic response of infants born to mothers with Fabry disease who are treated with Fabrazyme during lactation. The mothers will receive Fabrazyme treatment as part of the standard of care of Fabry disease and will be followed through the Fabry Registry.

Pregnant women who received Fabrazyme at any point during their pregnancy can be enrolled in the study. The mothers will receive Fabrazyme treatment (commercially available) at their currently prescribed dosage regimen as determined by their treating physician. If an enrolling woman is not receiving treatment with Fabrazyme at the Baseline visit, she should start treatment with Fabrazyme between the delivery and Month 1 visit.

Approximately 10 mothers and up to 10 infants will be enrolled in this study.

1.2 OBJECTIVES

1.2.1 Primary objectives

The primary objectives of this study are:

1. To determine whether α GAL activity is present in the breast milk of mothers with Fabry disease who are being treated with Fabrazyme during lactation.
2. To measure breast milk production and composition (volume, protein and fat content) in women with Fabry disease who receive Fabrazyme during lactation.
3. To determine whether Fabrazyme affects the growth, development, and immunologic response of infants born to mothers with Fabry disease who receive Fabrazyme during lactation.

1.2.2 Secondary objectives

NA

1.3 DETERMINATION OF SAMPLE SIZE

No formal statistical sample size calculations were performed for this study. The sample size of approximately 10 mothers and up to 10 infants is based upon 1) the availability of mothers to study lactation in this rare disease and 2) the availability of infants whose parents or legal guardians consent to their participation in this study.

1.4 STUDY PLAN

This study will evaluate the effects of Fabrazyme on lactation and on the growth, development, and immunologic response of infants born to mothers with Fabry disease who are treated with Fabrazyme during lactation. There are 3 participation scenarios: mother/infant full participation, mother full participation/infant development only, and mother full participation/infant no participation (see protocol Section 9.1).

Whether or not the mother continues to lactate will be assessed at each visit. Breast milk will be collected at Months 1, 3, and 6 immediately prior to Fabrazyme infusion, just after the end of the infusion, and 2 hours after the end of the infusion. Breast milk samples will be analyzed for volume, presence of α GAL activity, total fat content, and total protein concentration. Blood samples from the mother will be drawn for pharmacokinetic (PK) analysis prior to each breast milk collection. If infant genotyping is performed on the umbilical blood cord sample collected at Baseline visit, a buccal cell sample will be obtained from the mother to rule out contamination of the cord blood sample with maternal DNA.

If the parent(s)/legal guardian(s) consent to infant participation, the infant's growth and development will be assessed. The infant may also be tested for the formation or continued presence of serum IgG and IgM antibodies to r-h α GAL and for genotype.

For the purposes of this study, the mother and the infant will each be considered a study patient. The mother must be enrolled in the Fabry Registry and will be followed using the Fabry Registry assessment schedule and CRFs as well as this study's CRF. During this study, infants will be evaluated, ie, the infant may be tested for IgG and IgM antibodies to r-h α GAL at birth and Months 2, 6, and 12 and will be tested developmentally at each visit for 24 months, or until the parent(s)/legal guardian(s) withdraws consent and discontinues the infant's study participation, the infant is discontinued from the study by the Investigator (see Section 7.3.1), or the study is terminated (see Section 7.3.2).

If the mother is no longer lactating, the mother will discontinue this study but continue to be followed in the Fabry Registry. The infant will be followed for development only for the remainder of this 24-month study.

1.5 MODIFICATIONS TO THE STATISTICAL SECTION OF THE PROTOCOL

The statistical section of the protocol was never changed in an amendment.

The first patient was enrolled on August 29, 2006. After 5 mothers have contributed breast milk samples to this study, an interim analysis of α GAL activity in the breast milk will be performed. In addition, the status of this study will be summarized annually as part of the Fabry Registry Program Annual Report and the Fabrazyme Post-Marketing Commitment Annual Report..

1.6 STATISTICAL MODIFICATIONS MADE IN THE STATISTICAL ANALYSIS PLAN

NA

2 STATISTICAL AND ANALYTICAL PROCEDURES

2.1 ANALYSIS ENDPOINTS

2.1.1 Demographic and baseline characteristics

The baseline value is defined as within 1 month prior to delivery (mother) and at birth (infant).

All baseline safety parameters are presented along with the on-treatment summary statistics in the safety sections ([Section 2.4.5](#) and [Section 2.4.4](#)).

Demographic characteristics

Demographic variables are gender (Male, Female), race (white, Black, Asian, American Indian or Alaska Native, Native Hawaiian or other Pacific Island), age in years (quantitative), ethnicity (Hispanic or Latino, non-Hispanic or Latino).

Lactation Status

The mother's lactation status will be provided: Is the mother providing milk for the protocol? (Yes, No); Is the mother planning on breast feeding the infant(s)? (Yes, No).

Maternal cell contamination (MCC) analysis

If umbilical cord blood sample was collected and MCC analysis was performed, the results (Maternal Cell Contamination detected, No Maternal Cell Contamination detected) will be collected.

Medical history

Medical history (including Fabrazyme status during pregnancy) will be collected through the Registry.

This information will be coded using the version of Medical Dictionary for Regulatory Activities (MedDRA) currently in effect at Sanofi at the time of database lock.

Any technical details related to computation, dates, and imputation for missing dates are described in [Section 2.5](#).

2.1.2 Prior or concomitant medications

All medications taken from the time of signing the informed consent through study completion are to be reported in the case report form pages.

All medications will be coded using the World Health Organization-Drug Dictionary (WHO-DD) using the version currently in effect at Sanofi at the time of database lock.

Any technical details related to computation, dates, imputation for missing dates are described in [Section 2.5](#).

2.1.3 Efficacy endpoints

NA

2.1.3.1 Primary efficacy endpoint(s)

NA

2.1.3.2 Secondary efficacy endpoint(s)

NA

2.1.4 Safety endpoints

The safety analysis will be based on the reported adverse events (AEs) and other safety information, such as physical examinations, etc.

The following study variables will be summarized as appropriate for the mothers (items marked with * will be collected through the Registry):

- Medical history (including Fabrazyme status during pregnancy)*
- Genotyping*
- Pregnancy outcome*
- IgG antibody status*
- Lactation status
- Plasma and breast milk PK testing
- The level of α GAL, volume, and fat and protein content in breast milk samples
- Frequency of AEs
- Frequency of concomitant medications

The following study variables will be summarized as appropriate for the infants:

- Medical history
- Physical examination
- Gender

- Genotype
- Apgar score at 1 minute and 5 minutes after birth
- Denver II Developmental Screening Test
- IgM antibodies to r-hαGAL – presence, time to development, level of titers present
- IgG antibodies to r-hαGAL – presence, time to development, level of titers present
- Frequency of AEs
- Frequency of concomitant medications

Observation period

The on-study observation period is defined as the time from the signing of the informed consent until the end of the study (defined as last protocol planned patient contact by telephone approximately 28 days after the final study procedures are completed).

2.1.4.1 Adverse events variables

All AEs ongoing at the time of withdrawal, study termination, or study completion require a follow up at approximately 28 days after discontinuation of study participation. The Investigator will be asked to follow-up on all SAEs that were ongoing at the time of withdrawal, termination or completion until resolution, until both the sponsor and investigator agree follow-up is deemed no longer medically necessary or until the patient is lost to follow-up.

If any new SAEs are identified during the course of this follow-up of ongoing SAEs, additional follow-up of these new SAEs may be performed. The Investigator and sponsor will determine if the follow-up is clinically warranted and relevant to the evaluation of the safety of the trial treatment or until patient is lost to follow up. The investigator must follow patients with AEs until their condition resolves or stabilizes. Certain conditions that are not expected to resolve, such as metastatic cancer, need not be followed indefinitely by the investigator.

All adverse events (including serious adverse events) will be coded to a lower-level term (LLT), preferred term (PT), high-level term (HLT), high-level group term (HLGT), and associated primary system organ class (SOC) using the version of Medical Dictionary for Regulatory Activities (MedDRA) currently in effect at Sanofi at the time of database lock.

All occurrences of adverse events (including serious adverse) from the time of signed informed consent until the end of the study will be recorded.

2.1.4.2 Deaths

The deaths from the signing of the informed consent through the completion of the study will be recorded.

2.1.4.3 Laboratory safety variables

NA

2.1.4.4 Vital signs variables

NA

2.1.4.5 Electrocardiogram variables

NA

2.1.5 Pharmacokinetic variables

Pharmacokinetic Sampling

α GAL concentrations will be measured from Blood and breast milk samples taken from the mothers. Blood samples will be taken from the mother at Months 1, 3, and 6 for PK testing (if mother is lactating at the time of the evaluation and is receiving Fabrazyme therapy).

Bioanalytical Method

Plasma and milk α GAL concentrations will be quantified by measuring enzyme activity using a fluorometric assay with a lower limit of quantification of 1.38 ng/mL. The assay does not differentiate between endogenous α GAL and Fabrazyme.

Pharmacokinetic parameters

The following pharmacokinetic parameters will be calculated, using noncompartmental methods from plasma α GAL concentrations and milk α GAL concentrations

- maximum plasma concentration observed (C_{max}) in plasma and milk
- area under the plasma α GAL concentration versus time curve calculated using the trapezoidal method from 0 to 2 hours post end of infusion ($AUC_{0-2 \text{ plasma}}$).
- the amount of α GAL in milk calculated as the product of α GAL activity times the milk volume
- area under the milk α GAL concentration versus time curve calculated using the trapezoidal method from 0 to 2 hours post end of infusion ($AUC_{0-2 \text{ milk}}$).

- lactation clearance determined in the 0-2 hours interval, according to the following equation: amount of α GAL excreted over the sampling period divided by the AUC during the sampling period

The milk to plasma ratio for AUC₀₋₂ will also be computed.

2.2 DISPOSITION OF PATIENTS

This section describes patient disposition for both patient study status and the patient analysis populations.

Screened patients are defined as any patient who met the inclusion criteria and signed the informed consent. Enrolled patients are defined as any patient who signed the informed consent and participated in at least one study visit.

For patient study status, the total number of patients in each of the following categories will be presented in the clinical study report using a flowchart diagram or summary table:

- Screened patients
- Screen failure patients and reasons for screen failure
- Patients who did not complete the study treatment period as per protocol
- Patients who discontinued study treatment by main reason for permanent treatment discontinuation
- Status at last study contact

For all categories of patients (except for the screened and nonrandomized categories) percentages will be calculated using the number of enrolled patients as the denominator. Reasons for treatment discontinuation will be supplied in tables giving numbers and percentages by treatment group.

A patient is considered lost to follow-up at the end of the study if he/she is not assessed at the last protocol planned visit.

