### **6.2.2 Study Duration**

This study will last for up to 2 years (24 months).

If the mother is no longer lactating or the mother is no longer receiving Fabrazyme treatment, the mother will discontinue this study but continue to be followed in the Fabry Registry. The infant will be followed, for development only, for the remainder of this 24 month study.

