### 7.3 WITHDRAWAL CRITERIA

#### 7.3.1 Patient Withdrawal

The mother (or the legal guardian acting on behalf of the infant and/or the mother) is free to withdraw consent and discontinue her participation as well as the infant's participation in the study at any time, without prejudice to further treatment. The mother and infant's participation in the study may be discontinued at any time at the discretion of the Investigator. The following may be justifiable reasons for the Investigator to remove a patient from the study:

Mother:

- The mother is uncooperative/noncompliant and will not adhere to study responsibilities, including failure to appear at scheduled study visits, or failure to undergo study assessments, and/or failure to comply with the Registry schedule of assessments.
- The mother was erroneously included in the study.
- The mother experiences an intolerable AE.
- The mother stops lactating.
- The study is terminated by the Sponsor.

Infant:

- The mother and/or infant was erroneously included in the study.
- The infant experiences an intolerable AE.
- The study is terminated by the Sponsor.

If the mother and/or the infant discontinues participation in the study, or their participation is discontinued by the Investigator, the mother and/or infant's legal guardian should be contacted by the Study Investigator in order to obtain information about the reason(s) for discontinuation and collection of any potential AEs. Whenever possible the patient should return to the study site for the final clinical assessments as specified in [Section 9.1.1.8](#), [Section 9.1.2.8](#), or [Section 9.1.3.4](#), as appropriate. The Study Investigator will describe the reason for discontinuation on the appropriate CRF.

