### 9.1 MEASUREMENTS ASSESSED AND STUDY FLOWCHART

After obtaining signed, written informed consent, the study will be conducted as outlined in the following sections. [Table 1](#) summarizes the schedules of study evaluations at each study visit for mothers and infants enrolled for full participation (eg, full/full participation through Month 24). If the mother is enrolled for full participation but the infant is enrolled only for developmental assessments (eg, full/development) (see [Table 2](#)), the mother and infant schedules are the same as full/full participation, except the infant blood samples are omitted. If only the mother is participating in the study (eg, full/no) (see [Table 3](#)), her assessment schedule is the same as full participation except study participation is stopped and considered complete at Month 6. Refer to the Study Operations Manual (SOM) for guidelines regarding test assessments and procedures for handling/shipment of all laboratory samples.

The timing of study procedures will be based on calendar weeks starting with Baseline; defined for the mother as during the month prior to delivery and at birth for the infant. Thus Month 1 is 1 month postpartum. The study procedures and assessments are scheduled so that the maximum time the mother and the infant may participate in the study is approximately 24 months.

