#### **9.1.1.8 Month Twenty-four/End of Study (Full/Full Participation)**

The following assessments will be completed at Month 24 (24 months  $\pm$ 7 days postpartum) or at early withdrawal:

Mother:

- Record lactation status.
- Record AEs.
- Record concomitant medications.

Infant:

- Conduct a physical examination.
- Administer the Denver II Developmental Screening Test.
- Record status of receiving breast milk.
- Record AEs.
- Record concomitant medications.

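### SAP 2.2 can label a mother who left under the protocol's own exit rule as lost to follow-up, and the protocol and SAP end SAE recording about 28 days apart

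*SAP*

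**What the plan says.** **Disposition.** SAP 2.2 states that a patient is "considered lost to follow-up at the end of the study if he/she is not assessed at the last protocol planned visit". For the status categories, apart from screened patients, "percentages will be calculated using the number of enrolled patients as the denominator". The listed categories include discontinuation of study treatment and status at last contact. None covers leaving the study because lactation ended.

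**Maternal exit.** SAP 1.4 says: "If the mother is no longer lactating, the mother will discontinue this study but continue to be followed in the Fabry Registry". Protocol 6.1 has the same rule. Protocol 6.2.2 is wider: "If the mother is no longer lactating or the mother is no longer receiving Fabrazyme treatment, the mother will discontinue this study". Against this, Tables 1 and 2 give the mother visits at Months 12, 18 and 24, and protocol 9.1 says that "the maximum time the mother and the infant may participate in the study is approximately 24 months". In the mother-only scenario (Table 3) the last visit is Month 6.

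**Leaving early.** Protocol 7.3.1 asks for a closing visit, but not as a firm requirement: "Whenever possible the patient should return to the study site for the final clinical assessments". It points to 9.1.1.8, 9.1.2.8 and 9.1.3.4, which apply at the scheduled month "or at early withdrawal". It also says: "The Study Investigator will describe the reason for discontinuation on the appropriate CRF".

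**SAE window.** Protocol 9.4.2 records SAEs from consent through the Month 24 visit, or the Month 6 visit if only the mother takes part; for early leavers it stops at the last study visit. Protocol 9.4.12 plans a telephone call to all participants about 28 days after the final procedures, covering adverse events. SAP 2.1.4 defines the end of the study as that call, and SAP 2.1.4.1 has all adverse events, serious ones included, recorded until then.

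**The concern.** The lost-to-follow-up label should mark people whose outcome is unknown. Here a mother can leave because the protocol tells her to, have her reason on the CRF, be reached by telephone at the point that the SAP itself calls the end of the study, and still meet the SAP's definition of lost. In a study of about 10 mothers a few such cases would change how complete the follow-up looks. Protocol 11.5 plans counts of discontinued and completed patients but does not say which of the two a protocol-directed exit is.

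The SAE mismatch matters for a different reason. Two staff following different sections could handle the same late event differently, so the SAE tables would depend on which section was applied.

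**Working it through.** The documents state no calculated figure on this point, so the check is mainly a comparison of texts.

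**Step 1. Apply SAP 2.2 to each way a mother can end participation.**

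| Path | Last planned visit attended? | Reached about 28 days later? | Result under SAP 2.2 |
|---|---|---|---|
| A. Completes Month 24 (Month 6 if mother-only) | Yes | Either | Not lost |
| B. Lactation or Fabrazyme ends; attends the early-withdrawal End of Study visit | Yes, if that visit counts | Either | Reasonably not lost; the SAP is silent |
| C. Lactation or Fabrazyme ends; misses that visit; reason on CRF | No | Yes | Lost, by the words |
| D. Leaves; no reason, no visit, no call | No | No | Lost, correctly |

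Paths C and D receive the same label. Path B depends on a reading that SAP 2.2 does not give.

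**Step 2. Look for another rule that rescues path C.** The treatment-discontinuation category does not fit a mother who stops lactating but stays on Fabrazyme. Status at last contact is listed without defined levels. Protocol 11.5 does not define a planned exit.

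**Step 3. Size per case.** Inputs: about 10 mothers (protocol 11.2, SAP 1.3); enrolled patients as denominator (SAP 2.2); mothers and infants summarized separately (protocol 11.5).

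- Shift per path-C mother = 1/n. With n = 10: 1/10 = 10 points.
- With n = 5, the smallest number for which SAP 2.4 plans summaries rather than listings: 1/5 = 20 points.
- If SAP 2.2 were taken to pool 10 mothers and 10 infants: 1/20 = 5 points.

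The documents do not say how many mothers will follow path C, so no total is given.

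**Step 4. Apply the SAE texts to one case.** Suppose a patient completes the Month 24 visit and a new SAE begins 20 days later (an assumed date), first reported on the call.

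- Protocol 9.4.2: outside the recording period.
- Protocol 9.4.12: inside the planned adverse event assessment.
- SAP 2.1.4 and 2.1.4.1: inside the observation period, so recorded.

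The conflict is therefore partly within the protocol itself. Size of the gap, taking 30.4375 days per month and counting from delivery:

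- 28/(24 × 30.4375) = 28/730.5 = 3.8% of a 24-month follow-up.
- 28/(6 × 30.4375) = 28/182.6 = 15.3% of a 6-month follow-up.

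The documents give no SAE rate, so the number of affected events cannot be estimated.

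**The case against.** The strongest defense of SAP 2.2 is that the protocol already plans the exit visit. Protocol 7.3.1 sends a leaver to the End of Study assessments, and those sections say that they apply at early withdrawal. The natural reading is that this is the leaver's last planned visit. Month 24 can also be read as a maximum for mothers who are still lactating. The exit reason is on the CRF, and the SAP lists status at last contact. This stands for path B. A reader might infer that every mother who stops lactating will be reported as lost; the documents do not support that. What remains is path C, and the SAP's silence on path B.

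It is also fair to say that little depends on the label. There is no hypothesis testing and no imputation (protocol 11.1), and adverse event percentages use the safety population (SAP 2.4.5.1). The effect is confined to the disposition report.

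On SAEs, protocol 9.4.1 follows ongoing events after exit and allows follow-up of new SAEs found while ongoing SAEs are being followed. This narrows the gap. It does not cover a patient with no ongoing SAE whose first SAE is reported on the call.

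A reader might go further and infer that the infant adverse event tables are wrong because they do not separate time on breast milk from later time. The documents do not support that either. Objective 3 names growth, development and immunologic response rather than adverse events, and the protocol plans no such split. Milk-fed time is also always the younger age, so a split could not separate milk from age.

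**Conclusion.** Both points hold as minor faults of wording.

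1. SAP 2.2 as written counts as lost a mother who left under the exit rule, missed the closing visit and was reached by telephone. Each such case is worth about 10 points, assuming about 10 enrolled mothers reported separately from infants. The total is unknown and could be zero if every leaver attends the early-withdrawal visit and that visit is counted.
2. The SAE recording period ends at two different times, about 28 days apart, and whether a new SAE first reported on the call is recorded is unsettled. Which end point should apply is for the sponsor to decide; the sections must agree.

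Neither point affects a hypothesis test, because none is planned.

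**What to change.** **SAP 2.2.** State that the End of Study assessment held at early withdrawal counts as the last planned visit. Define lost to follow-up as leaving with no recorded reason and no final contact, whether by visit or by the 28-day call. Add a disposition category, *planned exit: lactation or Fabrazyme ended*, filled from the CRF reason.

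**Protocol and SAP.** Reconcile protocol 9.4.2 with protocol 9.4.12 and SAP 2.1.4 and 2.1.4.1. Reconcile the maternal exit text with the Month 24 maternal schedule in Tables 1 and 2, including the difference between protocol 6.1 and SAP 1.4 (lactation only) and protocol 6.2.2 (lactation or Fabrazyme).

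**Optional, and not the correction of an error.** Add one by-infant listing of AE and SAE onset date and age against the milk status recorded at the preceding and following visits, with the following visit blank if there is none. Label it descriptive, because milk exposure is confounded with infant age and milk status is only a proxy for Fabrazyme exposure.

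**Cost.** The SAP changes are a few sentences and one table row. The discontinuation reason is already collected and the call is already planned. The outcome of the call must be recorded for the new definition to work; the SAP's last-contact status implies that it is, but the documents do not show the form. The protocol reconciliation needs an amendment. The listing, if added, uses milk status and event dates that the study already collects.
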